7.2.2. Patient Background and Treatment History of Mycobutin

- **Patient background**

For the safety analysis set, (preventive) effectiveness analysis set, and (therapeutic) effectiveness analysis set, the following patient background factors will be tabulated in accordance with Section 7.1:

- Sex [male, female]
- Pregnancy (only in females) [absent, present]
- Age (continuous)
- Age group 1 [<15 years, ≥15 years to <65 years, ≥65 years]
- Age group 2 [<20 years, ≥20 years to <30 years, ≥30 years to <40 years, ≥40 years to <50 years, ≥50 years to <60 years, ≥60 years to <70 years, ≥70 years to <80 years, ≥80 years]
- Body weight (continuous)
- Body weight group [<40 kg, ≥40 kg to <50 kg, ≥50 kg to <60 kg, ≥60 kg to <70 kg, ≥70 kg, unknown]
- Inpatient/outpatient [inpatient, outpatient, mixture of inpatient and outpatient]
- Route of infection [blood preparation, vertical transmission, medical accident, others (including sexual transmission), unknown]
- Primary disease [HIV infection, others]
- Race [Japanese, others]
- Allergy [absent, present, unknown]

- Complications [absent, present]
- Hemophilia (A/B) as a complication [absent, present]
- Renal dysfunction as a complication: [absent, present]
- Hepatitis A as a complication [absent, present]
- Hepatitis B as a complication [absent, present]
- Hepatitis C as a complication [absent, present]
- Other hepatic dysfunction as a complication [absent, present]
- Syphilis as a complication [absent, present]
- Other condition as a complication: [absent, present]
- Ophthalmologic complications [absent, present]
- Concomitant use of SMX/TMP [absent, present]
- Concomitant therapy [absent, present]
- Use of medications other than Mycobutin [absent, present]
- Baseline HIV-RNA copy number (copies/mL) [<200 , ≥ 200 to <400 , ≥ 400 to $<10,000$, $\geq 10,000$ to $<100,000$, $\geq 100,000$, unknown]
- Baseline CD4 count (cells/mm³) [≥ 0 to <100 , ≥ 100 to <200 , ≥ 200 to <350 , ≥ 350 to <500 , ≥ 500 , unknown]
- Centers for Disease Control and Prevention (CDC) classification [A, B, C, P-0, P-1, P-2, unknown]

In the safety analysis set, the number and percentage of relevant patients will be tabulated for the following characteristic by system organ class (SOC) and preferred term (PT):

- Complications

In the safety analysis set and effectiveness analysis sets, the number and percentage of relevant patients will be tabulated for the following characteristics:

- Concomitant medications other than anti-HIV drugs
- Non-drug concomitant therapies

- **Status of treatment of Mycobutin**

In the safety analysis set, the exposure of patients to Mycobutin will be tabulated with respect to the following status of treatment:

- Duration of treatment * [≤ 1 week, >1 week to ≤ 2 weeks, >2 weeks to ≤ 4 weeks, >4 weeks to ≤ 8 weeks, >8 weeks to ≤ 12 weeks, >12 weeks to ≤ 24 weeks, >24 weeks to ≤ 36 weeks, >36 weeks to ≤ 1 year, >1 year to ≤ 3 years, >3 years to ≤ 6 years, >6 years to ≤ 8 years, >8 years]
- Duration of one prophylactic or therapeutic treatment [≤ 1 week, >1 week to ≤ 2 weeks, >2 weeks to ≤ 4 weeks, >4 weeks to ≤ 8 weeks, >8 weeks to ≤ 12 weeks, >12 weeks to ≤ 24 weeks, >24 weeks to ≤ 36 weeks, >36 weeks to ≤ 1 year, >1 year]
- Maximum daily dose [<150 mg, 150 mg, 300 mg, 450 mg, >450 mg]

- Mean daily dose [<150 mg, 150 mg, >150 mg to <300 mg, 300 mg, >300 mg to <450 mg, 450 mg, >450 mg]
- Continued or discontinued
- Reason of the use of Mycobutin [MAC (therapeutic), MAC (prophylactic), tuberculosis, Nontuberculous Mycobacteriosis (NTM Infections) other than MAC]

The duration of treatment is defined as the period from the first to the last confirmed dose of Mycobutin during this survey, and does not include the period during which Mycobutin is suspended.

7.2.3. Safety Analysis

7.2.3.1. Adverse Drug Reactions

- **Adverse drug reactions**

The number and percentage of patients with adverse drug reactions will be tabulated by SOC and PT.

- **Serious adverse drug reactions**

The number and percentage of patients with serious adverse drug reactions will be tabulated by SOC and PT.

The number and percentage of patients with serious adverse drug reactions will also be tabulated separately for expected and unexpected reactions by SOC and PT.

- **Other details of adverse drug reactions**

The number and percentage of patients with adverse drug reactions will be tabulated for the following aspects by SOC and PT:

- Seriousness [serious, non-serious]
- Expected/unexpected [expected, unexpected]
- Time to onset [≤ 1 week, >1 week to ≤ 2 weeks, >2 weeks to ≤ 4 weeks, >4 weeks to ≤ 8 weeks, >8 weeks to ≤ 12 weeks, >12 weeks to ≤ 24 weeks, >24 weeks to ≤ 36 weeks, >36 weeks to ≤ 1 year, >1 year]
- Outcome [death, sequela, not recovered, recovering, recovered, unknown]

If the same AE (the same PT) occurs more than once in the same patient, it will be handled as follows in the tabulation of the number of patients with events:

- Seriousness: If at least one event is reported as serious, they are counted as a serious event.
- Expected/unexpected: If at least one event is reported as unexpected, they are counted as an unexpected event.
- Time to onset: The time to the first onset will be used.

- Outcome: The outcome for the last event will be used. For multiple-time occurrence in the same fiscal year, the outcome for the severest event should preferably be used.

- **Major investigation items**

For the following major investigation items, the number and percentage of patient who experienced each event will be tabulated:

- Hematologic disorders (including anemia, decreased platelets, decreased white blood cells, and pancytopenia)
- Uveitis

The number and percentage of patients who experienced the events of major investigation items will also be tabulated for different outcomes by SOC and PT.

In addition, the number and percentage of patients who experienced the events of major investigation items will be tabulated with respect to whether they concomitantly used the drugs contraindicated for coadministration, those for which precautions should be taken for coadministration (e.g., some of azoles and macrolides), or SMX/TMP and with respect to the concomitant drug's dose by SOC and PT.

- **Adverse drug reactions by patients of included in/excluded from the safety analysis set**

In patients for whom the case report form was collected, the listing of adverse drug reactions in patients excluded from the safety analysis set will be prepared. The number of patients with adverse drug reactions will also be tabulated by SOC and PT.

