1.1. Study Design

As part of the HRD Joint Survey, this study includes HIV patients for whom Mycobutin is prescribed, including those captured in retrospective surveys. As far as possible, this part of the HRD joint Survey seeks to include all patients who receive Mycobutin at participating medical institutions. The indications and dosage and administration for Mycobutin, the survey periods, and the major investigation items are presented below.

- *Indications*

Susceptible strains: Mycobacteria susceptible to Mycobutin

Indications: Tuberculosis, nontuberculous mycobacteriosis including Mycobacterium avium complex (MAC) infection, and prevention of symptoms of disseminated MAC infection in HIV patients.

- *Dosage and Administration*

Tuberculosis:

For adults, an oral dose of rifabutin 150 mg to 300 mg is administered once daily.

For adults with multi-drug resistant tuberculosis, an oral dose of rifabutin 300 mg to 450 mg is administered once daily.

Treatment of nontuberculous mycobacteriosis including MAC infection:

For adults, an oral dose of rifabutin 300 mg is administered once daily.

Prevention of symptoms of disseminated MAC infection in HIV patients:

For adults, an oral dose of rifabutin 300 mg is administered once daily.

- *Survey Periods*

Tuberculosis and nontuberculous mycobacteriosis including MAC infection:

The survey will start on October 7, 2008, and the registration of patients will end at the end of the fiscal year after the 6th year.

Patient registration: October 7, 2008 - March 31, 2015

Prevention of the symptoms of disseminated MAC infection in HIV patients:

The survey will start on October 7, 2008, and the registration of patients will end at the end of the fiscal year after the 8th year.

Patient registration: October 7, 2008 - March 31, 2017

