1.2. Study Objectives

The objectives of the study are to grasp the following aspects and to assess whether a specified drug use-results survey or a post-marketing clinical study is needed:

- *Unexpected adverse drug reactions*
- *Incidence of adverse drug reactions under the actual use, and*
- *Factors considered to affect the safety and/or effectiveness, etc.*

In this survey, the incidence of hematologic disorders (including anemia, decreased platelets, decreased white blood cells, and pancytopenia) and uveitis will be assessed as the major investigation items.

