5.4. Covariates

In the analysis of safety, the presence or absence of contraindicated for coadministration (e.g., some azoles and macrolides) noted in PRECAUTIONS of the package insert as the drugs that require precautions for coadministration will be used as a covariate.

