7.2.3.4. Subgroup Analysis

The number and percentage of patients who experienced at least one adverse drug reaction will be tabulated for each factor specified in Section 4.5. The statistical tests stated in Section 7.1 will be performed to evaluate the association between the patient background factors and development of adverse drug reactions.

The number and percentage of patients who experienced adverse drug reactions will be tabulated by SOC and PT for each of the subgroups defined by the following factor:

- Reason for the use of Mycobutin [MAC (therapeutic), MAC (prophylactic), tuberculosis, NTM other than MAC]

Similar analysis will also be performed for serious adverse drug reactions and SAEs.

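### The only planned table relating uveitis and hematologic disorders to interacting drugs does not account for Mycobutin dose, so it can hide or create an apparent interaction if that dose affects risk and differs between users and non-users

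*SAP*

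**What the plan says.** SAP section 1.2 singles out two groups of events: "the incidence of hematologic disorders (including anemia, decreased platelets, decreased white blood cells, and pancytopenia) and uveitis will be assessed as the major investigation items". Section 7.2.3.1 tabulates them overall and by outcome. It then says that patients with these events "will be tabulated with respect to whether they concomitantly used the drugs contraindicated for coadministration, those for which precautions should be taken for coadministration", "or SMX/TMP and with respect to the concomitant drug's dose by SOC and PT". The only dose named there is that of the concomitant drug.

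Mycobutin dose appears elsewhere in the SAP:

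- Section 1.1 gives the labelled doses. For tuberculosis: "For adults, an oral dose of rifabutin 150 mg to 300 mg is administered once daily". For multi-drug resistant tuberculosis: "For adults with multi-drug resistant tuberculosis, an oral dose of rifabutin 300 mg to 450 mg is administered once daily". The two other labelled uses, therapy for nontuberculous mycobacterial disease (MAC among them) and prevention of disseminated MAC, both carry 300 mg.
- Section 7.2.2 tabulates it as exposure: "Maximum daily dose [<150 mg, 150 mg, 300 mg, 450 mg, >450 mg". Mean daily dose is also listed.
- Section 4.5 makes maximum and mean daily dose safety subgroup factors. Section 7.2.3.4 applies those factors as follows: "The number and percentage of patients who experienced at least one adverse drug reaction will be tabulated for each factor specified in Section 4.5". It extends this to serious adverse drug reactions and serious adverse events.

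The one safety covariate, in section 5.4, is whether a patient received interacting drugs, described as those "noted in PRECAUTIONS of the package insert as the drugs that require precautions for coadministration". Section 7.1.3 offers percentages, exact confidence intervals, Fisher's exact test and the exact Cochran-Armitage test. It gives no stratified or adjusted method.

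**The concern.** Users and non-users of an interacting drug are not randomised. Comparing their event percentages says something about the interaction only if their Mycobutin exposure is similar, or if the difference in exposure is shown. The planned table does neither, and no other planned table crosses these events with Mycobutin dose.

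The survey aims to identify factors affecting safety, and the SAP's version history says that SMX/TMP was added in version 3.0 in order to look at its interaction with Mycobutin. Uveitis and hematologic disorders are the events the survey singles out. A crude table that looks reassuring, or alarming, because of the dose mix could mislead those who read the reexamination report. A reassuring one would also give nobody a reason to run a further analysis.

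**Working it through.** The documents give no sample size, event rate, dose-risk relation or Mycobutin dose by coadministration, so there is no planned figure to reproduce. What follows is an illustration on assumed inputs.

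**Inputs (all assumed).** Two Mycobutin dose levels. Risk at the lower level r = 2%. Risk ratio between higher and lower dose d = 1.5 to 4. True risk ratio for coadministration within each dose level θ = 2.0 (an interaction) or 1.0 (none). Share at the higher dose: p₁ in users and p₀ in non-users of the interacting drug.

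**Formula.**

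- Crude risk in users = θ × r × [p₁d + (1 − p₁)]
- Crude risk in non-users = r × [p₀d + (1 − p₀)]
- Crude ratio = θ × [1 + p₁(d − 1)] / [1 + p₀(d − 1)]

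The baseline risk r cancels, so the 2% does not affect the ratio.

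**One case in full (d = 3, so 2% and 6%).**

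- Interaction present (θ = 2), p₁ = 20%, p₀ = 80%. Users: 0.8 × 4% + 0.2 × 12% = 5.6%. Non-users: 0.2 × 2% + 0.8 × 6% = 5.2%. Crude ratio 1.08 against a true 2.0.
- No interaction (θ = 1), p₁ = 80%, p₀ = 20%. Users: 0.2 × 2% + 0.8 × 6% = 5.2%. Non-users: 0.8 × 2% + 0.2 × 6% = 2.8%. Crude ratio 1.86 against a true 1.0.

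**Range, true ratio 2.0, users less often at the higher dose.** Columns are p₁/p₀ in percent.

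| d | 40/60 | 30/70 | 20/80 |
|---|---|---|---|
| 1.5 | 1.85 | 1.70 | 1.57 |
| 2 | 1.75 | 1.53 | 1.33 |
| 3 | 1.64 | 1.33 | 1.08 |
| 4 | 1.57 | 1.23 | 0.94 |

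**Range, true ratio 1.0, users more often at the higher dose.**

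| d | 60/40 | 70/30 | 80/20 |
|---|---|---|---|
| 1.5 | 1.08 | 1.17 | 1.27 |
| 2 | 1.14 | 1.31 | 1.50 |
| 3 | 1.22 | 1.50 | 1.86 |
| 4 | 1.27 | 1.63 | 2.13 |

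With d = 1, or with p₁ = p₀, the crude ratio equals θ and nothing is distorted.

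**Effect of stratifying (d = 3, 1,000 users and 1,000 non-users).**

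- Interaction present. Lower dose: 32/800 users, 4/200 non-users. Higher dose: 24/200 users, 48/800 non-users. Mantel-Haenszel ratio = (32 × 200/1000 + 24 × 800/1000) / (4 × 800/1000 + 48 × 200/1000) = 25.6/12.8 = 2.00.
- No interaction. Lower dose: 4/200 users, 16/800 non-users. Higher dose: 48/800 users, 12/200 non-users. Ratio = (4 × 800/1000 + 48 × 200/1000) / (16 × 200/1000 + 12 × 800/1000) = 12.8/12.8 = 1.00.

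**The case against.** The strongest reply is that the imbalance is supposed, not shown. Nothing in the documents says that patients on interacting drugs receive a different Mycobutin dose, or that either event depends on dose. Of the four reasons for use in section 7.2.2, three share a labelled 300 mg; only tuberculosis varies. This stands, and it limits the point to a possibility. The 1.08 above also comes from an extreme split: with the same threefold dose effect, 30/70 gives 1.33 and 40/60 gives 1.64.

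A reader might infer that the SAP ignores Mycobutin dose. It does not. Dose is a subgroup factor for any adverse drug reaction, serious reactions and serious adverse events. Section 7.2.3.4 breaks reactions down by event term within each reason for use, which shows these events by infection. The section 8 listings cover major-item events, Mycobutin administration and concomitant medications, and section 7.2.3.5 allows extra analyses. None of these is a prespecified table of the major items by coadministration and Mycobutin dose, and extra analyses are reported only if judged important.

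A reader might also infer that the survey's interaction conclusion will rest on this table. Section 3 makes tests exploratory and sets no decision rule. The crude percentage also validly describes incidence at the doses actually prescribed; it is the user versus non-user contrast that needs the dose split.

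Finally, the concomitant dose split might be taken to pool milligrams of unrelated drugs. The wording refers to the drug in the singular and can be read as drug by drug, so the documents do not support that reading as a defect.

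**Conclusion.** The gap is real: the single planned table linking the major investigation items to interacting drugs takes no account of Mycobutin dose, and no method in the plan adjusts for it. Whether this distorts the comparison depends on two conditions that the documents leave unquantified: a dose-risk relation, and a different dose mix in users and non-users. If both hold to the assumed degree, the crude ratio could be anywhere from mildly off (1.85 for a true 2.0; 1.08 for a true 1.0) to seriously wrong (0.94 and 2.13). If either fails, it is correct.

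The documents do not support a claim that the table will mislead, or in which direction. Because the analysis is descriptive, the harm would be a misleading table and not a false confirmatory claim. The point is worth acting on because the variable is already categorised and the change is small.

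**What to change.** In SAP section 7.2.3.1, add a tabulation of each major investigation item by coadministration (yes/no) within the existing Mycobutin maximum daily dose categories, collapsing categories where sparse. Define the dose in the same way for patients with and without events. Assigning dose at onset to cases and dose during overlap to the rest would not work: patients who were not coadministered have no overlap period, and exposure would then be defined by outcome. Show counts and exact 95% confidence intervals, as section 7.1.3 already allows. Give a Mantel-Haenszel risk ratio stratified by that dose only where counts allow, labelled as descriptive.

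The cost is a few lines of SAP text and one added stratification on a variable the SAP already tabulates. There are two drawbacks. Cells may be sparse, since no sample size is stated and the events may be few. Maximum daily dose may also not be the dose in force during coadministration, so some confounding by dose could remain.

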			
disease are collected in one-year unit.
 
 -The analysis of the content of past history was deleted, because it was found that the content of past history is not included in the collected data. - Minor erroneous descriptions were corrected. 
7.2.3.1 Adverse Drug Reactions
 
 -Tabulation of the number and percentage of patients with serious adverse drug reactions counted for expected and unexpected reactions separately was added. -The analysis of the measures taken for adverse drug reactions was deleted, because those data are collected as comments in the common case report form, and the determination of appropriate category from comment data is infeasible. 
7.2.3.2. Adverse Events
 
 -To provide basic results, tabulation of the number and percentage of patients with non-serious adverse events was added. 
8. LISTINGS
 
 -Listings presented in the text of the periodic safety update reports and the application for reexamination were identified and indicated as “for intext”. 
9. REFERENCES
 
 - “Standard Specifications of the Analysis for the HRD Joint Survey” was added.
3.0	21-DEC-2015	PPD	
Status of investigation: Patient registration and investigation ongoing
 
To investigate the drug interaction with SMX/TMP, analysis of safety and effectiveness in terms of the presence or absence of concomitant use of SMX/TMP was added to the following sections:
 
 - 4.5 Subgroups -7.2.2. Patient Background and Treatment History of Mycobutin -7.2.3.1. Adverse Drug Reactions 
-8. LISTINGS
 
Others
 
 -In 8. LISTINGS, duplication of “Listing of patients with adverse events” was corrected.
4.0	24-JUN-2016	PPD	
Status of investigation: Patient registration and investigation ongoing

Version	Date	Author(s)	Summary of Changes/Comments

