4.5. Subgroups

Subgroup analyses of safety will be performed for the following patient background factors:

- Sex [male, female]
- Pregnancy (in females) [absent, present]
- Age group 1 [<15 years, ≥15 years to <65 years, ≥65 years]
- Age group 2 [<20 years, ≥20 years to <30 years, ≥30 years to <40 years, ≥40 years to <50 years, ≥50 years to <60 years, ≥60 years to <70 years, ≥70 years to <80 years, ≥80 years]
- Primary disease [HIV infection, others]
- Race [Japanese, others]
- Hepatic dysfunction [absent, present]
- Hepatitis [absent, present]
- Renal dysfunction [absent, present]
- Past history [absent, present]
- Complications [absent, present]
- Ophthalmologic complications [absent, present]
- Baseline HIV-RNA copy number (copies/mL) [<200, ≥200 to <400, ≥400 to <10,000, ≥10,000 to <100,000, ≥100,000]
- Baseline CD4 count (cells/mm³) [≥0 to <100, ≥100 to <200, ≥200 to <350, ≥350 to <500, ≥500]
- Centers for Disease Control and Prevention (CDC) classification [A, B, C, P-0, P-1, P-2]

Subgroup analyses of safety will also be performed for the following other factors:

- Maximum daily dose [<150 mg, 150 mg, 300 mg, 450 mg, >450 mg]
- Mean daily dose [<150 mg, 150 mg, >150 mg to <300 mg, 300 mg, >300 mg to <450 mg, 450 mg, >450 mg]
- Duration of treatment [≤1 week, >1 week to ≤2 weeks, >2 weeks to ≤4 weeks, >4 weeks to ≤8 weeks, >8 weeks to ≤12 weeks, >12 weeks to ≤24 weeks, >24 weeks to ≤36 weeks, >36 weeks to ≤1 year, >1 year to ≤3 years, >3 years to ≤6 years, >6 years to ≤8 years, >8 years]
- Concomitant medications (anti-HIV drugs) [absent, present]
- Concomitant medications (anti-MAC drugs) [absent, present]

- Concomitant use of the combination of sulfamethoxazole and trimethoprim (SMX/TMP) [absent, present]

Subgroup analyses of effectiveness will be performed for the following patient background factors:

- Sex [male, female]
- Pregnancy (in females) [absent, present]
- Age group 1 [<15 years, ≥15 years to <65 years, ≥65 years]
- Age group 2 [<20 years, ≥20 years to <30 years, ≥30 years to <40 years, ≥40 years to <50 years, ≥50 years to <60 years, ≥60 years to <70 years, ≥70 years to <80 years, ≥80 years]
- Primary disease [HIV infection, others]
- Race [Japanese, others]
- Hepatic dysfunction [absent, present]
- Renal dysfunction [absent, present]
- Past history [absent, present]
- Complications [absent, present]
- Baseline HIV-RNA copy number (copies/mL) [<200, ≥200 to <400, ≥400 to <10,000, ≥10,000 to <100,000, ≥100,000]

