7.1.3. Analysis of Binary Data

Binary variables will be calculated by frequency and percentage. Confidence intervals (CIs) for the percentages may also be calculated; in this case, the 95% CIs (two-sided) will be calculated using an exact method. Statistical tests may also be performed when appropriate; an association with a nominal variable will be tested by Fisher's exact test, and an association with an ordinal variable by the exact Cochran-Armitage test.

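### The SMX/TMP safety comparison is crude: baseline CD4 is collected, but it is neither shown by SMX/TMP use nor adjusted for, so confounding by HIV disease stage can be neither seen nor removed

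*SAP*

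**What the plan says.** The SAP's version 3.0 history entry gives the reason for text that is still in force: "To investigate the drug interaction with SMX/TMP, analysis of safety and effectiveness in terms of the presence or absence of concomitant use of SMX/TMP was" inserted into the sections that it names.

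The current plan then provides two safety analyses by SMX/TMP.

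- **Section 7.2.3.1, major investigation items.** The outcomes are uveitis and "Hematologic disorders (including anemia, decreased platelets, decreased white blood cells, and pancytopenia"). Patients with these events are counted by whether they took contraindicated or precaution co-medication "or SMX/TMP and with respect to the concomitant drug's dose by SOC and PT". No test, strata or model is named.
- **Sections 4.5 and 7.2.3.4.** The factor is "Concomitant use of the combination of sulfamethoxazole and trimethoprim (SMX/TMP) [absent, present"]. Any ADR is tabulated for each factor separately, with similar tables for serious ADRs and SAEs. On testing, "The statistical tests stated in Section 7.1 will be performed to evaluate the association between the patient background factors" and ADRs. Under Section 7.1.3, "an association with a nominal variable will be tested by Fisher's exact test"; for ordered factors such as CD4 band the rule is "an association with an ordinal variable by the exact Cochran-Armitage test". Both tests are unadjusted.

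Disease stage is available. Protocol Section 5 collects HIV-RNA, CD4 and CDC class, and SAP Appendix A1.1 fixes their baseline as on or before the first dose. SAP Section 4.5 lists "Baseline CD4 count (cells/mm³") in five bands as a safety factor in its own right. Section 7.2.2 tabulates these variables for each whole analysis set, not by SMX/TMP use. Section 5.4 declares one safety covariate, contraindicated or precaution co-medication, and Section 7 names no stratified or regression method.

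**The concern.** In this survey SMX/TMP is prescribed by clinical choice. By listing CD4 in Section 4.5, the SAP treats it as a possible determinant of ADRs. If SMX/TMP use is also related to CD4, users and non-users differ in ADR risk for a reason unrelated to SMX/TMP. The crude percentages can then show a difference that is not due to the drug, or hide one that is.

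Testing CD4 as a separate factor does not help, because that table does not adjust the SMX/TMP contrast. Nor does any planned table show whether users and non-users differ in CD4, so a reader could not judge whether the problem is present.

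Hematologic disorders and uveitis are the survey's major investigation items, and finding factors that affect safety is an objective in both documents. Per Protocol Section 1, results go to reexamination and to yearly feedback for healthcare professionals.

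**Working it through.** **Figure to reproduce.** None. The documents state no sample size, power, event rate, share using SMX/TMP or CD4 distribution by use. All inputs below are assumptions, shown as a range.

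**Crude risk ratio when SMX/TMP has no effect.** Let pU and pN be the share of users and of non-users with low CD4, and k the ADR risk ratio for low against higher CD4. Risk within a CD4 stratum is the same with or without SMX/TMP, so the stratum-specific ratio is 1 by construction. The higher-CD4 risk cancels:

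crude RR = [pU·k + (1 − pU)] / [pN·k + (1 − pN)]

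| pU | pN | k | Substitution | Crude RR |
|---|---|---|---|---|
| 0.6 | 0.5 | 1.5 | 1.30 / 1.25 | 1.04 |
| 0.7 | 0.4 | 2 | 1.70 / 1.40 | 1.21 |
| 0.8 | 0.3 | 2 | 1.80 / 1.30 | 1.38 |
| 0.8 | 0.3 | 3 | 2.60 / 1.60 | 1.63 |
| 0.9 | 0.2 | 3 | 2.80 / 1.40 | 2.00 |

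Exchanging pU and pN inverts each ratio (1.25/1.30 = 0.96 to 1.40/2.80 = 0.50). The documents do not fix the direction, so masking is as open as a false signal.

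**How often a false signal would appear.** Simulation with no true effect: 2,000 surveys per row, half the patients users, 5% risk at higher CD4. Fisher's exact test on the crude table is set against a Mantel-Haenszel test stratified by CD4. The p<0.05 mark is a yardstick only; the SAP sets no significance level.

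| N | pU / pN | k | Crude Fisher | CD4-stratified |
|---|---|---|---|---|
| 200 | 0.7 / 0.4 | 2 | 5.2% | 5.2% |
| 200 | 0.8 / 0.3 | 3 | 16.8% | 4.7% |
| 500 | 0.7 / 0.4 | 2 | 8.1% | 4.5% |
| 500 | 0.8 / 0.3 | 2 | 16.6% | 4.8% |
| 500 | 0.8 / 0.3 | 3 | 42.3% | 4.9% |
| 1000 | 0.8 / 0.3 | 2 | 29.4% | 5.4% |
| 1000 | 0.8 / 0.3 | 3 | 71.5% | 5.3% |

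Median stratified odds ratios across all simulated settings were 0.98 to 1.02.

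**Reading.** With a moderate imbalance and a small survey there is no excess of false signals. With a strong imbalance, a threefold risk gradient and a larger survey, the excess is large. Stratifying by CD4 removes it here because CD4 is the only confounder in the assumed set-up.

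**The case against.** The strongest defence is that the plan is descriptive. Section 3.1 says that the study is not confirmatory and that p-values are descriptive, and Section 3.2 sets no decision rules. Section 1.2 aims to decide whether a further survey or study is needed, and a crude table can serve as a first screen for that. The interaction purpose appears in the version history, not in Sections 1.2 or 7.2.3.1. Section 7.2.3.5 allows further analyses, and Section 8 lists SMX/TMP users individually.

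This lowers the weight of the point but does not answer it. Exploratory status governs how p-values are read, whereas confounding shifts the percentages themselves. The further analyses are optional, unspecified and reported only if judged important.

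Three stronger readings are tempting, and the documents do not support them.

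- **That SMX/TMP users are sicker.** No section says that use varies with CD4, or in which direction. Listing CD4 in Section 4.5 makes it a factor to examine, as sex and race are.
- **That a crude Fisher test will decide the matter.** Section 7.2.3.1 names no test for uveitis or hematologic disorders. Section 7.2.3.4 assigns tests to background factors. Section 4.5 places SMX/TMP among the other factors, while Section 7.2.2 lists it with background. An unadjusted Fisher test for any ADR is therefore arguable, and no more.
- **That CD4 adjustment would isolate an interaction.** Under Section 4.1 every patient in the safety set received Mycobutin, so SMX/TMP's own effect stays mixed with any interaction. Reason for use, Mycobutin dose and other co-medication would also remain unadjusted.

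**Conclusion.** The point holds as an omission. The SAP compares ADRs, hematologic disorders and uveitis by SMX/TMP use only crudely, although baseline CD4 is collected, banded and listed as a safety factor. The planned tables can neither reveal nor remove confounding by disease stage.

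The size in this survey is unknown. Under the assumed inputs the crude risk ratio with no true effect is about 1.04 to 2.0, or the reciprocals if the imbalance runs the other way. The excess of false signals runs from none (5.2% against 5.2%) to large (71.5% against 5.3%). Possible bias is shown; actual bias is not. The conclusion depends on SMX/TMP use and ADR risk both varying with CD4, which the documents leave open.

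The change is worth making because the data are already coded and the comparison has a stated purpose. It does not undermine a confirmatory result, since the plan has none.

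**What to change.** In Sections 7.2.3.1 and 7.2.3.4:

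1. Tabulate baseline CD4, HIV-RNA and CDC class by SMX/TMP use in the safety analysis set.
2. For any ADR and for hematologic disorders, and for uveitis if events allow, give a Mantel-Haenszel or exact common odds ratio with 95% CI beside the crude figure. Stratify by baseline CD4 collapsed to <100, 100 to <200 and ≥200 cells/mm³; these are unions of the existing bands.
3. Show patients with unknown CD4 separately. Section 6 allows no imputation, and a stratum of unknowns cannot be taken as homogeneous in CD4.
4. State that the result is a CD4-adjusted association and not evidence of an interaction, because all patients received Mycobutin.

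The cost is one or two extra tables from variables already collected. The downside is wide or inestimable intervals for rare events, uveitis possibly among them; where that happens, give the stratum counts without a pooled estimate.
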